16.2.4. Exploratory Immunogenicity Variables

The exploratory immunogenicity analyses will be performed for the Month 3 and Month 7 PPS.

16.2.4.1. ANTI-HPV IGG ANTIBODY CONCENTRATION BETWEEN GROUP ASSESSMENT Anti-HPV IgG antibody concentration at Month 3 and Month 7 for each antigen.

For each antigen an adjusted GMC and GMC ratio with 2-sided 95% CI for intervention group which is derived from an ANOVA model on log10 transformed concentration will be tabulated for anti-HPV IgG antibody concentration adjusted for country effect. The analysis will be performed at Month 3 and at Month 7, summarised for the pre-vaccination status of seronegative, seropositive and total. The model will be based on the data from all groups, will include study group and country as a fixed effect and will be based on the PPS. The non-inferiority of different vaccine formulations to the control group will be assessed if the lower limit of the 2-sided 95% CI is not less than the defined non-inferiority limit. The non-inferiority between different vaccine formulations will also be assessed.

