Blood sample collection:

- A 5 mL blood sample will be drawn from Step 1 (Sentinel) participants at Visit 1 (Day 1) and Visit 2 (Day 7) to assess biochemical and hematological parameters.
- For assessment of immune response, blood samples (~50 mL) will be drawn at Day 1, Month 2, Month 3, Month 6, Month 7 and Month 12 in all participants. Immunoglobulin G (IgG) antibody determination will be performed for these timepoints in all participants. Pseudovirion-based neutralization assays will be performed. Blood samples drawn at Day 1 (all participants), Month 2 (at least 96 participants in each group), Month 3 (all participants) and Month 7 (at least 150 participants in each group) will be tested.

Study	Number of	Number of Age	Study	Blinding*	
groups	participants	(Min-Max)	vaccinations	Visit 1 to Visit 7 (Observer- Blind)	
HPV9High	270	16-26 years of age	HPV9-High	X	
HPV9Med	270	16-26 years of age	HPV9-Medium	X	
HPV9Low	270	16-26 years of age	HPV9-Low	X	
Gar9	270	16-26 years of age	Gardasil 9	X	

Table 5 Study Groups, Vaccines, and Blinding

Note: In Germany, only adult participants between and including 18 to 26 years of age will be included in this clinical study.

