9.4.2.2.2. Exploratory Between Group Assessment

For each HPV antigen, antibody GMC ratios and the 2-sided 95% CIs of antibody GMC ratios will be computed using an analysis of variance model on the log10 transformation of the antibody concentration adjusted for country effect. This analysis will be performed at Month 3 (1-month post-dose 2) and at Month 7 (1-month post-dose 3) time points. The non-inferiority of different vaccine formulations to the control group will be assessed if the lower limit of the 2-sided 95% CI is not less than the defined non-inferiority limit.

Additional exploratory group comparisons may be performed to facilitate the formulation selection.

9.4.3. iSRC Analyses

The analysis will be based on the ES. The analyses will be further described in detail in the statistical analysis plan.

- Demographic characteristics, baseline general medical and vaccination history, withdrawals from the study.
- Study intervention exposure by group and by intervention.
- Summary tables containing information on any events considered in the holding rules and other events (SAE, any withdrawal due to intervention-related AE, any AEs causing withdrawal from the study).
- Incidence of solicited administration site AEs (pain, redness, swelling): any grade, Grade 3 (2-days or more after Dose 1, 7-day follow-up period after intervention), any solicited administration site AEs leading to hospitalization within 7 days (Day 1 Day 7) after each vaccine dose.

- Incidence of solicited systemic AEs (fever, headache, fatigue, myalgia, and arthralgia): any grade, Grade 3, any related, Grade 3 related (2-days or more after Dose 1, 7-day follow-up period after each intervention), any solicited systemic AEs leading to hospitalization, fever >40°C (104°F), within 7 days (Day 1 Day 7) after each vaccine dose).
- Incidence of unsolicited AEs: any, Grade 3, any related, Grade 3 related (7-day and 30-day follow-up period after each intervention).
- Any, Grade 3 or above abnormality in pre-specified hematology and biochemistry parameters with an event onset within 7 days (Day 1 Day 7) after each vaccine dose.
- Incidence of SAEs: Any, any related, fatal, fatal related.
- Incidence of pIMDs: Any, any related.
- Any medically attended events.
- Any pregnancy and pregnancy outcomes, overall and pregnancy exposures (i.e., exposures during pregnancy).

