7.6. Common Calculations

Geometric Mean Concentration/Titer (GMC/GMT):

Distributions of antibodies are generally skewed to the right (Nauta, 2010). Therefore, prior to any statistical analysis that assumes normally distributed observations, antibody concentrations or titers will be log10-transformed. GMC/GMTs and their 95% CI are computed by exponentiating (base 10) the least squares mean and 95% CI of the log10 titers.

Document: \\quintiles.net\Enterprise\Apps\sasdata\SASb\SAS\GlaxoSmithKline\HPV\213749

(HPV9)\Biostatistics\Documentation\SAP\GSK 213749(HPV9-AS04-

001)_WZA97329_SAP_Final_v3.0_02FEB2024.docx

Author: PPD Version Number: 3.0

Version Date: 02FEB2024

Template No.: CS_TP_BS016 Revision 7 Reference: CS_WI_BS005

Page 29 of 48

The GMC/GMT will be calculated using the following formula:

$$10^{\left(\frac{\sum_{i=1}^{n}\log 10(t_i)}{n}\right)}$$

Where $t_1, t_2, ..., t_n$ are n observed immunogenicity concentrations/titer.

Concentration below assay cut-off (i.e., <lower limit of quantification or < LLOQ) will be replaced by half the assay cut-off (LLOQ/2) for the purpose of GMC computation. Any concentrations above the upper limit of quantification (or ULOQ) will be set to the ULOQ value. No imputation for ULOQ will be performed for the sensitivity analysis of GMC/GMT and for the correlations and Deming's regression.

Seroconversion:

Defined as the appearance of antibodies (i.e., concentrations/titers greater than or equal to the cut-off value) in the serum of participants seronegative before vaccination.

For quantitative measurements, change from baseline will be calculated as:

• Test Value at Visit X – Baseline Value

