8. STATISTICAL CONSIDERATIONS

8.1. Adjustments for Covariates and Factors to be Included in Analyses

For details on the factors to be used in the analysis refer to section 17.1 and 17.2. The model will include all groups and country as fixed categorical effects in the ANOVA model.

Document: \\quintiles.net\Enterprise\Apps\sasdata\SAS\\SAS\GlaxoSmithKline\HPV\213749

(HPV9)\Biostatistics\Documentation\SAP\GSK_213749(HPV9-AS04-

001)_WZA97329_SAP_Final_v3.0_02FEB2024.docx

Author: PPD Version Number: 3.0

Version Date: 02FEB2024

Template No.: CS_TP_BS016 Revision 7 Reference: CS_WI_BS005

Page 30 of 48

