16.2.4.2. ANTI-HPV IGG ANTIBODY SEROCONVERSION RATE

The differences in the seroconversion rate at Month 3 and Month 7 will be summarized for each antigen between each HPV9 study group (High, Medium and Low) against Gardasil 9 along with the corresponding 2-sided 95% CI will be reported. The differences in the seroconversion rate at Month 3 and Month 7 between each antigen and HPV9 study group will also be assessed.

Document: \quintiles.net\Enterprise\Apps\sasdata\SAS\SAS\GlaxoSmithKline\HPV\213749

(HPV9)\Biostatistics\Documentation\SAP\GSK_213749(HPV9-AS04-

001)_WZA97329_SAP_Final_v3.0_02FEB2024.docx

Author: PPD Version Number: 3.0

Version Date: 02FEB2024

Template No.: CS_TP_BS016 Revision 7 Reference: CS_WI_BS005

Treference Treference

Page 39 of 48

16.2.4.3. ANTI-HPV NEUTRALIZING ANTIBODY TITERS BETWEEN GROUP ASSESSMENT Anti-HPV neutralizing antibody titers at Month 3 and Month 7 (at least 150 participants in each group) for each antigen.

For each antigen an adjusted GMT and GMT ratio with 2-sided 95% CI for intervention group which is derived from an ANOVA model on log10 transformed titer will be tabulated for anti-HPV neutralizing antibody titer adjusted for country effect. The analysis will be performed at Month 3 and at Month 7, summarised for the prevaccination status of seronegative, seropositive and total. The model will be based on the data from all groups, will include study group and country as a fixed effect and will be based on the PPS. The non-inferiority of different vaccine formulations to the control group will be assessed if the lower limit of the 2-sided 95% CI is not less than the defined non-inferiority limit. The non-inferiority between different vaccine formulations will also be assessed.

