Pre-vaccination	HPV9 Group	Gardasil 9 Group	Group GMC Ratio		
status	N Adjusted GMC	N Adjusted GMC	Value 95% CI		

Source: Listing xx.x.x.x

Abbreviations: HPV = Human Papillomavirus. GMC = Geometric Mean Concentration.

N = Number of participants with available results

The analysis is based on ANOVA model with log10 transformed anti-gE antibody concentration values as response variable and the study group and country as fixed effects.

Seronegative is defined as the situation where antibodies are not elevated (i.e, concentrations less than the LLOQ) in the serum of participants.

Seropositive is defined as the appearance of antibodies (i.e, concentrations greater than or equal to the LLOQ) in the serum of participants.

95% CI GMC = 95% confidence interval derived using the log-transformed antibody concentration.

The concentration below the assay cut-off will be replaced by half the cut-off (LLOQ/2). Concentration above the ULOQ will be replaced by the ULOQ

Programming Notes

[Source: \\quintiles.net\Enterprise\Apps\sasdata\SASb\SAS\GlaxoSmithKline\HPV\213749

(HPV9) \Biostatistics\Filename.sas] IQVIA DDMMMYYYY HH:MM

Output ID: IM0003

Document: \(\quintiles.net\Enterprise\Apps\sasdata\SASb\SAS\GlaxoSmithKline\HPV\213749 (HPV9)\Biostatistics\Documentation\SAP\Shells\\\ GSK 213749(HPV9-AS04-001) WZA97329 TFL Shells \(\forall V3.0 \) 05FEB2024.docx

Author: Version Number: 3.0

Table 14.2.2.1.2: Ratio of anti-HPV IgG Antibody GMCs for each antigen at Month 3 and Month 7 between HPV Groups (Per Protocol Set)

GSK Vaccines Page X of Y

Study 213749 - DELIVERY DESIGNATION

Table 14.2.2.1.2 Ratio of anti-HPV IgG Antibody GMCs for each antigen at Month 3 and Month 7 between HPV Groups Per Protocol Set

Pre- vaccination		First Group		First Group		Second Group		Group GMC Ratio		
status		N	Adjusted GMC	N A	Adjusted GMC	Value	95%	CI		
Seronegative	anti-HPV IgG concentration at Month 3									
beronegaerve	HPV9 High / HPV9 Medium	ХХ	XX.X	XX	XX.X	XX.X	xx.x;	XX.X		
	HPV9 Medium / HPV9 Low	XX	XX.X	XX	XX.X	XX.X	xx.x;	XX.X		
	HPV9 High / HPV9 Low	XX	XX.X	XX	XX.X	XX.X	xx.x;	XX.X		
Seropositive	anti-HPV IgG concentration at Month 3									
-	HPV9 High / HPV9 Medium	XX	XX.X	XX	XX.X	xx.x	xx.x;	XX.		
	HPV9 Medium / HPV9 Low	XX	XX.X	XX	XX.X	XX.X	xx.x;	XX.X		
	HPV9 High / HPV9 Low	XX	XX.X	XX	XX.X	XX.X	xx.x;	XX.		
Total	anti-HPV IgG concentration at Month 3									
	HPV9 High / HPV9 Medium	XX	XX.X	XX	XX.X	XX.X	xx.x;	XX.X		

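### The GMC and GMT ratio models that inform formulation selection adjust for country only and leave out the Day 1 antibody level, which is measured in every participant

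*SAP*

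**What the plan says.** All the documents agree on the model. Protocol 9.4.2.2.2 uses an "analysis of variance model on the log10 transformation of the antibody concentration adjusted for country effect". SAP 8.1, the covariate section, says: "The model will include all groups and country as fixed categorical effects in the ANOVA model". SAP 16.2.4.1 (IgG) says that the model "will include study group and country as a fixed effect and will be based on the PPS". SAP 16.2.4.3 repeats this for neutralizing titers, with ratios "derived from an ANOVA model on log10 transformed titer will be tabulated for anti-HPV neutralizing antibody titer adjusted for country effect". The footnote to shell Table 14.2.2.1.1 has log10 antibody values "as response variable and the study group and country as fixed effects", and the other three ratio-table shells match it in substance. No section adds a Day 1 level or a Day 1 serostatus term.

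Each ratio is reported for three sets by pre-vaccination status: seronegative, seropositive and total.

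The baseline value is planned for everyone. For IgG, Protocol 4.1 says: "Immunoglobulin G (IgG) antibody determination will be performed for these timepoints in all participants". The same section, and Protocol Appendix 3, plan the Day 1 neutralization assay in all participants. SAP 16.2.1.3 could be read as attaching the minimum of 150 per group to Day 1 as well, but Protocol 4.1 and Appendix 3 tie that minimum to Month 7.

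**The concern.** The ratios are exploratory, but Protocol 9.1 and 9.2.2.1 give them a purpose: to help choose the phase 3 formulation. A formulation meets the IgG criterion only if the lower confidence limit clears the margin on all nine HPV types, so precision per type matters.

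The pre-vaccination level of the same antigen in the same assay is a natural covariate for the post-vaccination level. Any variance it explains now stays in the residual and widens the intervals. This applies where Day 1 varies, which is in the total and seropositive sets. The power statement uses all 216 evaluable women per group with no deduction for women seropositive at Day 1, so it refers to the total set.

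The total ratio is also not corrected for a chance imbalance in Day 1 level or serostatus. The stratum tables would show such an imbalance but would not remove it from the total ratio.

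**Working it through.** **Inputs (Protocol 9.2.2 and 9.2.2.1).** Equal true means; one-sided 2.5% for each formulation; overall power taken as 1 − 9β, where β is the type II error for one HPV type. Three scenarios:

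- A: IgG, SD 0.7, margin 0.5, 216 per group (Table 18)
- B: IgG, SD 0.47, margin 0.67, 216 per group
- C: Month 7 titers, SD 0.6, margin 0.5, 120 per group

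**Reproducing the plan's figures.** SE = SD × √(2/n); noncentrality = −log10(margin)/SE; noncentral t with 2n − 2 degrees of freedom.

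- A: SE = 0.7 × √(2/216) = 0.0674; 0.3010/0.0674 = 4.47; β = 0.62%; overall 94.4% (protocol 94.6%)
- B: SE = 0.0452; 0.1739/0.0452 = 3.85; β = 3.02%; overall 72.8% (protocol 73%)
- C: SE = 0.0775; 0.3010/0.0775 = 3.89; β = 2.80%; overall 74.8% (protocol 74%)

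The protocol's figures are reproduced, and none is wrong.

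**Adding Day 1 to the total model.** Let r be the (multiple) correlation of the Day 1 terms with the post-vaccination log10 value. With k = 2 added terms and N women over four groups:

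residual variance = SD² × (1 − r²) × [1 + k/(N − 4 − k − 1)], with 2n − 2 − k degrees of freedom.

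The bracket is the cost of estimating the added terms. It is 1 + 2/857 = 1.0023 for IgG (N = 864) and 1 + 2/473 = 1.0042 for titers (N = 480).

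The documents do not give r, so a range is assumed:

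| r | CI narrowing, √(1 − r²), before term cost | Equivalent n for 216 | A | B | C |
|---|---|---|---|---|---|
| No Day 1 terms | – | 216 | 94.4% | 72.8% | 74.8% |
| 0 | 0% | 216 | 94.3% | 72.5% | 74.3% |
| 0.1 | 0.5% | 218 | 94.7% | 73.7% | 75.4% |
| 0.2 | 2.0% | 225 | 95.6% | 77.1% | 78.6% |
| 0.3 | 4.6% | 237 | 97.0% | 82.2% | 83.5% |

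Equivalent n is 216/(1 − r²).

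**Plausibility of the range.** If only serostatus carries information, r = log10(fold difference) × √(q(1 − q))/SD, where q is the share seropositive at Day 1. The values of q and fold are illustrations, not trial data:

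- q = 5%, 1.5-fold: r from 0.05 (SD 0.7) to 0.08 (SD 0.47)
- q = 10%, 2-fold: r from 0.13 to 0.19
- q = 20%, 3-fold: r from 0.27 to 0.41

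**Chance imbalance.** With r = 0.2, SD 0.7 and 216 per group, a Day 1 imbalance of 1.96 SE moves the unadjusted total ratio by a factor of 10^(0.2 × 1.96 × 0.0674) = 1.06.

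**Seronegative set.** A value below the cut-off "will be replaced by half the assay cut-off (LLOQ/2) for the purpose of GMC computation" (SAP 7.6), so Day 1 is constant in this set and there is nothing to adjust for.

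**The case against.** The strongest reply is that nothing is broken. The protocol, SAP and shells agree; the unadjusted ratio is unbiased and its interval valid under randomization; and the analysis is labelled exploratory. All of that stands.

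The gain also depends on an unknown r. Eligibility (at most four lifetime partners, no previous HPV vaccination, no history of a positive HPV test) probably keeps the seropositive share low, and in the total set r comes only from that minority. At r = 0.1 the net gains are 0.3, 0.9 and 0.6 points in A, B and C. Scenario A, with the stated margin of 0.5, already has about 94% power. Scenario B uses an alternative margin, and C is the minimum planned for Month 7 titers. Summing the nine type II errors is itself conservative: if the types were independent, B and C would start at 75.8% and 77.4%. No gain has been quantified for the seropositive set. These points limit the size of the benefit but do not remove it.

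Reporting by serostatus handles baseline within the seronegative set, but it does not adjust the total ratio. Protocol 9.4.2.2.2 allows further exploratory comparisons, but an adjusted ratio added on that basis would not be prespecified.

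Timing is a real constraint. SAP version 3.0 is dated February 2024, and the Month 3 interim analysis provides results by unblinded group. The documents do not say whether that analysis had been run. If it had, replacing the main model afterwards would weaken prespecification, and the supportive route would be the cleaner one.

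**Conclusion.** The concern holds as a loss of efficiency in a valid model; it is not an error or a bias. Under an assumed r of 0.1 to 0.3, common to all nine types, adjustment adds 0.3 to 2.6 points of overall power in the Table 18 scenario. It adds 0.9 to 9.4 points for IgG at margin 0.67, and 0.6 to 8.7 points for titers with 120 per group. If Day 1 predicts nothing, the loss is at most about 0.5 points (74.8% to 74.3%). The benefit therefore lies mainly in the two scenarios that start near 73–75%. The figures apply to the total set. Confidence is medium, because r and the Day 1 seropositive share are not in the documents. The change is worth making because the data are already planned, the downside is small and the ratios inform formulation selection.

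**What to change.** In SAP 8.1, 16.2.4.1 and 16.2.4.3, specify the models by set:

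1. **Total:** study group, country, log10 Day 1 value of the same antigen and assay (LLOQ/2 if below LLOQ), and a Day 1 serostatus indicator.
2. **Seropositive:** study group, country and log10 Day 1 value.
3. **Seronegative:** unchanged.

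List the change in SAP 4.3 as a difference from Protocol 9.4.2.2.2, and update the footnotes of Tables 14.2.2.1.1, 14.2.2.1.2, 14.2.2.4.1 and 14.2.2.4.2.

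If the sponsor prefers to keep the protocol model as the main one, or if group-level Month 3 results have already been seen, prespecify the Day 1-adjusted total ratios as a supportive analysis instead.

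No new visit, sample or assay is needed. The work is model code, wording in three SAP sections, one line in SAP 4.3 and four footnotes. The statistical cost is two degrees of freedom in the total model and one in the seropositive model.

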16.2.4.2. ANTI-HPV IGG ANTIBODY SEROCONVERSION RATE

The differences in the seroconversion rate at Month 3 and Month 7 will be summarized for each antigen between each HPV9 study group (High, Medium and Low) against Gardasil 9 along with the corresponding 2-sided 95% CI will be reported. The differences in the seroconversion rate at Month 3 and Month 7 between each antigen and HPV9 study group will also be assessed.

Document: \quintiles.net\Enterprise\Apps\sasdata\SAS\SAS\GlaxoSmithKline\HPV\213749

(HPV9)\Biostatistics\Documentation\SAP\GSK_213749(HPV9-AS04-

001)_WZA97329_SAP_Final_v3.0_02FEB2024.docx

Author: PPD Version Number: 3.0

Version Date: 02FEB2024

Template No.: CS_TP_BS016 Revision 7 Reference: CS_WI_BS005

Treference Treference

Page 39 of 48

16.2.4.3. ANTI-HPV NEUTRALIZING ANTIBODY TITERS BETWEEN GROUP ASSESSMENT Anti-HPV neutralizing antibody titers at Month 3 and Month 7 (at least 150 participants in each group) for each antigen.

For each antigen an adjusted GMT and GMT ratio with 2-sided 95% CI for intervention group which is derived from an ANOVA model on log10 transformed titer will be tabulated for anti-HPV neutralizing antibody titer adjusted for country effect. The analysis will be performed at Month 3 and at Month 7, summarised for the prevaccination status of seronegative, seropositive and total. The model will be based on the data from all groups, will include study group and country as a fixed effect and will be based on the PPS. The non-inferiority of different vaccine formulations to the control group will be assessed if the lower limit of the 2-sided 95% CI is not less than the defined non-inferiority limit. The non-inferiority between different vaccine formulations will also be assessed.

16.2.4.4. ANTI-HPV NEUTRALIZING ANTIBODY SEROCONVERSION RATE

The differences in the seroconversion rate at Month 3 and Month 7 will be summarized for each antigen between each HPV9 study group (High, Medium and Low) against Gardasil 9 along with the corresponding 2-sided 95% CI will be reported. The differences in the seroconversion rate at Month 3 and Month 7 between each antigen and HPV9 study group will also be assessed.

16.2.4.5. COMPARISON OF ANTI-HPV IGG ANTIBODY CONCENTRATION AND ANTI-HPV NEUTRALIZING ANTIBODY TITERS

A qualitative comparison between the ant-HPV IgG antibody concentration and the anti-HPV neutralizing antibody titers will be performed for each antigen by timepoint on all the PPS (except Month 6 and Month 12). This will be performed on each timepoint and antigen where both the anti-HPV IgG antibody concentration and the anti-HPV neutralizing antibody titer will be available. The agreement rate of the 2 results will be summarized and presented along with the kappa and the kappa p-value. The larger the kappa value (close to 1) the better the agreement between the two tests. The McNemar p-value will also be summarized.

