	Correlation between anti-HPV IgG antibody concentration and anti-HPV neutralizing antibody titers at Day 1, Month 2, Month 3 and Month 7.

¹ Seroconversion is defined as the appearance of antibodies (i.e., concentrations/titer greater than or equal to the cut-off value) in the serum of participants seronegative before vaccination.

Note: Tertiary objectives and endpoints are available in the main text of this protocol.

Overall Design: This will be a phase 1/2 randomized, observer-blind, multi-country study with 4 groups of females 16-26 years of age at the time of vaccine administration. Participants will be

² At least 150 participants in each group. In case of any delay, analysis may be performed for as many participants as possible with data available at the time of the analysis. Analysis for remaining participants will be performed at the time of the next analysis.

³ 384 participants (at least 96 participants in each group)

randomized in a 1:1:1:1 ratio to receive a series of 3 investigational adjuvanted intervention doses (3 different potencies [a high, medium, low potency]) or a series of the *Gardasil 9* vaccine. The investigational adjuvanted intervention or *Gardasil 9* vaccine will be administered intramuscularly (IM) at Day 1 (Month 0), Month 2, and Month 6. Blood sampling will be performed on Day 1, Month 2, Month 3, Month 6, Month 7, and Month 12 to assess for immunological response. In Germany, only adult participants between and including 18 years to 26 years of age are to be included in this clinical study.

This study is organized in to 2 steps. Forty-eight participants (12 per group) of the study Step 1 (sentinel participants) will receive the initial assigned dose prior to participants in Step 2 of the study, and sentinel participants will have an additional blood sampling visit at Day 7 to assess for biochemical and hematological parameters. The internal Safety Review Committee (iSRC) will review the accumulated safety data up to 7 days post-dose 1 for the sentinel participants* to determine whether any of the pre-defined holding rules have been met. If no safety concerns were observed and no holding rules were met, the sentinel participants will continue with study visits and dosing as scheduled and the Step 2 participants will be initiated. Vaccination of Step 2 participants with a second dose will not be initiated before all Step 1 participants have received their second vaccination dose.

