The study also evaluates the **immune responses using a neutralization assay** as a secondary endpoint. If the standard deviation for log₁₀ transformed antibody titers is around 0.6 as observed in HPV-019 (109823) study assessing GSK's bivalent HPV-16/18 AS04-adjuvanted vaccine:

- the sample size of at least 150 participants to obtain 120 evaluable participants at Month 7 provides at least 74% power to assess the non-inferiority of a formulation to *Gardasil 9* in terms of neutralizing antibody geometric mean titers (GMTs) with a non-inferiority margin of 0.5.
- the sample size of at least 270 participants to obtain 216 evaluable participants provides at least 98% power to show the non-inferiority of a formulation to *Gardasil 9* in terms of neutralizing antibody GMTs with a non-inferiority margin of 0.5.

However, note that this does not take into account the multiplicity due to comparisons performed for antibody concentrations measured by ECL assay.

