Document: \\quintiles.net\Enterprise\Apps\sasdata\SAS\SAS\GlaxoSmithKline\HPV\213749 (HPV9)\Biostatistics\Documentation\SAP\Shells\\
GSK_213749(HPV9-AS04-001)_WZA97329_TFL Shells_V3.0_05FEB2024.docx
Version Number:

Author: Version Number: 3.0

Table 14.2.2.8 Summary of qualitative comparison between ECL and PBNA for each antigen by time point (Per Protocol Set)

GSK Vaccines Page X of Y

Study 213749 - DELIVERY DESIGNATION

Table 14.2.2.8

Summary of qualitative comparison between ECL and PBNA for each antigen by time point Per Protocol Set

	Antigen:	XXX										
Study dose	Visit	n	Pos/ Pos	Neg/ Nea	Pos/ Neg	Neg/ Pos	IgG % +ve	Neutralizing titers % +ve	Agreement rate %	Kappa	McNema p-value	Kappa p- value
study dose	VISIC	11	103	iveg	Neg	105	100	CICCIS 6 IVE	Tace o	карра	p value	varue
HPV9-High	Day 1	XX	XX	XX	XX	XX	XX	XX	XX	xx	0.xxx	0.xxx
	Month 2	XX	XX	XX	XX	XX	XX	XX	XX	XX	0.xxx	0.xxx
	Month 3	XX	XX	XX	XX	XX	XX	XX	XX	XX	0.xxx	0.xxx
	Month 7	XX	XX	XX	XX	XX	XX	XX	XX	XX	0.xxx	0.xxx
	Overall	XX	XX	XX	XX	XX	XX	XX	XX	XX	0.xxx	0.xxx
HPV9-Medium	Day 1	XX	XX	XX	XX	XX	XX	xx	XX	XX	0.xxx	0.xxx
	Month 2	XX	XX	XX	XX	XX	XX	XX	XX	XX	0.xxx	0.xxx
	Month 3	XX	XX	XX	XX	XX	XX	XX	XX	XX	0.xxx	0.xxx
	Month 7	XX	XX	XX	XX	XX	XX	XX	XX	XX	0.xxx	0.xxx
	Overall	XX	XX	XX	XX	XX	XX	XX	XX	XX	0.xxx	0.xxx

HPV9-Low Gardasil 9 Total

Abbreviations: HPV = Human Papillomavirus. ECL = Electrochemiluminescence assay. PBNA = pseudovirion-based neutralization assay.

Document:

\\quintiles.net\Enterprise\Apps\sasdata\SASb\SAS\GlaxoSmithKline\HPV\213749 (HPV9)\Biostatistics\Documentation\SAP\Shells\

GSK 213749(HPV9-AS04-001)_WZA97329_TFL Shells_V3.0_05FEB2024.docx

Author:

Version Number:

Version Date: 05FEB2024

3.0

n is the number of samples with both concentration and titer values are available.

Percentages are based on n.

Pos/Pos is the number of participants seropositive with both ECL and PBNA.

Neg/Neg is the number of participants seronegative with both ECL and PBNA.

Pos/Neg is the number of participants seropositive with ECL and seronegative with PBNA.

Neg/Pos is the number of participants seronegative with ECL and seropositive with PBNA.

Seronegative is defined as the situation where antibodies are not elevated (i.e, concentrations less than the LLOQ) in the serum of participants.

$\hbox{ Table 14.2.2.8} \\ \hbox{Summary of qualitative comparison between ECL and PBNA for each antigen by time point } \\ \hbox{Per Protocol Set}$

Antigen: xxx

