			Pos/	Neg/	Pos/	Neg/	IgG %	Neutralizing	Agreement		McNema	Kappa p-
Study dose	Visit	n	Pos	Neg	Neg	Pos	+ve	titers % +ve	rate %	Kappa	p-value	value

Seropositive is defined as the appearance of antibodies (i.e, concentrations greater than or equal to the LLOQ) in the serum of participants.

Programming Notes

Output ID: LS0014

[Source: \\quintiles.net\Enterprise\Apps\sasdata\SASb\SAS\GlaxoSmithKline\HPV\213749

(HPV9) \Biostatistics\Filename.sas] IQVIA DDMMMYYYY HH:MM

Document: \\quintiles.net\Enterprise\Apps\sasdata\SAS\SAS\GlaxoSmithKline\HPV\213749 (HPV9)\Biostatistics\Documentation\SAP\Shells\

GSK 213749(HPV9-AS04-001)_WZA97329_TFL Shells_V3.0_05FEB2024.docx

Author: Version Number: 3.0

Document:

\\quintiles.net\Enterprise\Apps\sasdata\SASb\SAS\GlaxoSmithKline\HPV\213749 (HPV9)\Biostatistics\Documentation\SAP\Shells\
GSK 213749(HPV9-AS04-001)_WZA97329_TFL Shells_V3.0_05FEB2024.docx

Version Number:

Version Number: 3.0 Author:

Document:

\\quintiles.net\Enterprise\Apps\sasdata\SASb\SAS\GlaxoSmithKline\HPV\213749 (HPV9)\Biostatistics\Documentation\SAP\Shells\
GSK 213749(HPV9-AS04-001)_WZA97329_TFL Shells_V3.0_05FEB2024.docx

Version Number:

Version Number: 3.0 Author:

05FEB2024 Version Date:

Table 14.3.1.1: Overall Summary of Grade 3 Solicited Administration Site Events and Solicited Systemic Events Reported within 7 days (Days 1-7) after each vaccine dose and overall (Exposed Set)

Page X
GSK Vaccines

of Y

Study 213749 - DELIVERY DESIGNATION

Table 14.3.1.1

Overall Summary of Grade 3 Solicited Administration Site Events and Solicited Systemic Events Reported within 7 days (Days 1-7) after each vaccine dose and overall Exposed Set

Period: After first vaccine dose / After second vaccine dose / After third vaccine dose / Overall (dose) / Overall (participant)

		HPV9 High (N=XXX)	HPV9 Medium (N=XXX)	HPV9 Low (N=XXX)	Gardasil 9 (N=XXX)	Total (N=XXX)
Any grade 3 solicited event	n (%)	x (x.x)	x (x.x)	x (x.x)	x (x.x)	x (x.x)
	[95% CI]	[xx.x,	[xx.x,	[xx.x,	[xx.x, xx.x]	[xx.x, xx.x]
	e	xx.x] x	xx.x] x	xx.x] x	x	x
Any grade 3 solicited administration site event	n (%)	x (x.x)	x (x.x)	x (x.x)	x (x.x)	x (x.x)
	[95% CI]	[xx.x,	[xx.x,	[xx.x,	[xx.x, xx.x]	[xx.x, xx.x]
	e	xx.x] x	xx.x] x	xx.x] x	x	x
Any grade 3 solicited systemic event	n (%)	x (x.x)	x (x.x)	x (x.x)	x (x.x)	x (x.x)
	[95% CI]	[xx.x,	[xx.x,	[xx.x,	[xx.x, xx.x]	[xx.x, xx.x]
	e	xx.x] x	xx.x] x	xx.x] x	x	x

Source: Listing xx.x.x.x

Document:

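### The SAP reads a larger kappa as better ECL/PBNA agreement at every visit, but if post-vaccination positivity is about 98-100% kappa can be near zero, negative or undefined despite 96-100% agreement

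*SAP*

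**What the plan says.** SAP 16.2.4.5 classifies each sample as positive or negative by ECL (IgG) and by PBNA (neutralizing titer) and compares the two results for each antigen. The visits are Day 1, Month 2, Month 3 and Month 7. On the statistics it says: "The agreement rate of the 2 results will be summarized and presented along with the kappa and the kappa p-value". A McNemar p-value is added. Kappa is the only statistic given an interpretation: "The larger the kappa value (close to 1) the better the agreement between the two tests". The section has no caveat on prevalence and no instruction for a table in which one assay has no negatives.

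The output is shell Table 14.2.2.8, "Summary of qualitative comparison between ECL and PBNA for each antigen by time point". For each group it has a row per visit and an Overall row, with the four cell counts, percent positive by each assay, the agreement rate, kappa and both p-values. Its footnote sets the cut-off: "Seropositive is defined as the appearance of antibodies (i.e, concentrations greater than or equal to the LLOQ".

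The analysis sits under the exploratory variables in SAP 16.2.4, although SAP Table A lists the same qualitative summary within a secondary estimand.

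**The concern.** Kappa rescales observed agreement by the agreement expected from the two marginal positivity rates. When both rates are close to 1, expected agreement is also close to 1. The denominator then almost vanishes, and one or two samples decide the value.

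A reader who applies the SAP sentence to such a table would read a kappa of 0 as poor concordance when the assays agree on nearly every sample. Comparing kappas across visits, antigens or groups would then mostly compare the number of negatives. The rule covers 9 antigens x 4 groups x 3 post-vaccination visits = 108 kappas, against 9 x 4 = 36 at Day 1.

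**Working it through.** **Inputs.** Month 7 PBNA planning is in Protocol 9.2.2.1: "the sample size of at least 150 participants to obtain 120 evaluable participants at Month 7", that is 150 x 0.8 = 120 per group. The Month 2 subset is at least 96 per group (Protocol 1.1). Full evaluable group size is 270 x 0.8 = 216 (Protocol 9.2.2). The documents state no expected kappa, agreement rate or positivity rate, so there is no planned figure to reproduce.

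**Formula.** With cells a = both positive, b = ECL positive only, c = PBNA positive only, d = both negative: po = (a+d)/n, p1 = (a+b)/n, p2 = (a+c)/n, pe = p1 x p2 + (1-p1)(1-p2), kappa = (po-pe)/(1-pe).

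**Step 1: agreement held at 96.7%, n = 120, two discordant each way.**

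| (a,b,c,d) | pe | kappa |
|---|---|---|
| (116,2,2,0) | 0.9672 | -0.017 |
| (114,2,2,2) | 0.9356 | 0.48 |
| (104,2,2,12) | 0.7939 | 0.84 |
| (58,2,2,58) | 0.5000 | 0.93 |

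First row in full: po = 116/120 = 0.9667; p1 = p2 = 118/120 = 0.9833; pe = 0.9833² + 0.0167² = 0.9672; kappa = (0.9667-0.9672)/(1-0.9672) = -0.017.

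**Step 2: one assay 100% positive.** If p1 = 1, then pe = p2. No sample is negative by ECL, so po = p2 as well. Kappa is therefore 0 if p2 < 1, and 0/0 if p2 = 1. Examples at n = 120: (119,1,0,0) has 99.2% agreement and kappa 0; (115,5,0,0) has 95.8% and kappa 0; (120,0,0,0) has 100% and no kappa.

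**Step 3: sensitivity to single samples.** At n = 120, (118,1,1,0) gives 98.3% agreement and kappa -0.008, (117,1,1,1) gives the same 98.3% and 0.49, (118,1,0,1) gives 0.66, and (119,0,0,1) gives 1.0. At n = 216, (214,1,1,0) gives 99.1% and -0.005, while (213,2,0,1) gives the same 99.1% and 0.50. The pattern at n = 96 is the same.

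**Step 4: range over assumed positivity.** Multinomial simulation, n = 120, 40,000 runs, equal positivity in both assays, between-assay correlation phi assumed. The table shows the share of 2x2 tables in which kappa is undefined or at most 0.2.

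| Positivity | phi 0 | phi 0.3 | phi 0.5 |
|---|---|---|---|
| 80% | 98% | 18% | 0.3% |
| 90% | 97% | 25% | 2% |
| 95% | 96% | 34% | 9% |
| 98% | 96% | 49% | 30% |
| 99% | 99% | 69% | 55% |
| 99.5% | 100% | 83% | 74% |

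At phi 0 the assays are unrelated, so a low kappa is correct at any positivity. The phi 0.3 and 0.5 columns isolate the prevalence effect. At 99% positivity and phi 0.5, mean agreement is 99.0%, yet 55% of tables fall in the low or undefined group and 33% give kappa above 0.6.

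**Step 5: the Overall row.** Take three post-vaccination visits of (118,1,1,0), each with kappa -0.008, and add 110 concordant negatives from Day 1, where kappa alone is undefined. The pooled table is (354,3,3,110): po = 464/470 = 0.987, pe = 0.635, kappa = 0.97. The pooled value is high because it mixes visits of different prevalence.

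**The case against.** The strongest reply is that the table already protects the reader. The agreement rate, all four cells and percent positive by each assay stand in the same row as kappa, so a table such as (118,1,1,0) shows 98% beside the kappa. The interpretation sentence has no threshold and triggers no decision. The quantitative comparison of the assays is made separately by Pearson correlation and Deming regression (SAP 16.2.3.5). All of this stands, and it keeps the point small. It does not remove the fault: kappa alone has a reading rule, the agreement rate has neither a rule nor a confidence interval, and no instruction covers an empty margin.

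A second reply is that the high-positivity premise is not documented. That is also right. A reader might infer that nearly all samples will be positive after vaccination, so that kappa must collapse at most visits. The documents do not support that. They give no seropositivity rate and no LLOQ value, and Protocol 9.2.2.1 says that no immunogenicity data exist yet for the IgG assay. Month 2 follows a single dose. One or two concordant negatives can lift kappa to about 0.5-1.0. The support is indirect: the cut-off is only the LLOQ, Month 3 and Month 7 follow doses 2 and 3, and SAP 16.2.3.1 and 16.2.3.3 plan counts above the ULOQ, including in participants seronegative at baseline.

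Third, negative percent agreement is no simple substitute. With no negatives it is 0/0. For (214,1,1,0), with either assay as reference, it is 0/1, with an exact 95% CI of 0 to 97.5%. The fix has to allow for this.

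**Conclusion.** The point holds conditionally. If post-vaccination positivity is about 98-100% in both assays, kappa can be near 0, negative or undefined with 96-100% agreement, and the SAP sentence would then be read the wrong way. If one assay is 100% positive, this is certain. At 98% positivity, 30-49% of simulated tables with moderate between-assay correlation (phi 0.5 to 0.3) give kappa undefined or at most 0.2; at 99% it is 55-69%. These shares rest on assumed positivity and correlation, not on figures in the documents.

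The kappa p-value has the same weakness. On the usual null of kappa = 0, which the SAP does not state, it would be non-significant or missing in tables with almost perfect agreement.

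It would go too far to say that good concordance is hidden, since the cells and agreement rate are shown, or that kappa is usable only at Day 1. The Overall row can have both categories populated, and Day 1 could have the mirror problem if positives are sparse. The primary GMC endpoint and the non-inferiority assessments are unaffected. This is a cheap, optional improvement.

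**What to change.** In SAP 16.2.4.5 and shell Table 14.2.2.8:

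- Make overall agreement and positive percent agreement, each with an exact 95% CI, the main concordance measures, and name the reference assay for the latter. For (116,2,2,0) positive agreement is 116/118 = 98.3% with either reference.
- Give negative percent agreement with its denominator, and only where negatives exist.
- Show kappa and its p-value only when both categories are populated in both assays; otherwise print not estimable.
- Replace the interpretation sentence with a statement that kappa depends on prevalence, must be read with the agreement rate, and is not comparable across visits or with the pooled Overall row. This is still needed after the display rule, because (118,1,1,0) meets that rule and gives -0.008.

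The cost is a few extra columns, a display condition and one edited sentence. No new data are needed, because the cell counts are already tabulated.
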